7.2.1.4 Assessment of Intensity

Intensity refers to the degree of discomfort or impairment associated with an event. The intensity of MEs/AEs is to be reported on the eCRF as mild, moderate, or severe, according to the definitions provided below. In addition, to maximize consistency in assessment, it is recommended that the National Cancer Institute (NCI) Common Terminology Criteria for Adverse Events (CTCAE) scale be used.

Intensity	Corresponding NCI CTCAE Grade
Mild: awareness of a sign or symptom but easily tolerated	1
Moderate : discomfort sufficient to cause interference with normal daily activities	2
Severe: resulting in inability to do work or perform normal daily activities	3–5

7.2.1.5 Serious Adverse Events

An SAE is an adverse event occurring at any dose that results in any of the following outcomes:

- Death
- A life-threatening adverse event
- Inpatient hospitalization or prolongation of existing hospitalization
- A persistent or significant disability or incapacity
- A congenital anomaly in the offspring of a patient who received the study treatment
- An important medical event that does not result in death, is not life-threatening, and does
 not necessitate hospitalization but which in the investigator's judgment may jeopardize
 the patient and may necessitate medical or surgical intervention to prevent one of those
 outcomes. Examples include allergic bronchospasm requiring intensive treatment in an
 emergency room or at home, blood dyscrasias or convulsions that do not result in
 inpatient hospitalization, or the development of drug dependency or treatment-related
 substance abuse.

Clarifications:

- "Life-threatening" means that the patient was, in the view of the investigator, at immediate risk of death from the event as it occurred. This definition does not include an event that, had it occurred in a more severe form, might have caused death.
- Hospitalization for elective treatment of a pre-existing condition that did not worsen during the study is not considered an AE.

- Complications that occur during hospitalization are AEs. If a complication prolongs hospitalization, the event is considered an SAE.
- "Inpatient" hospitalization means the patient has been formally admitted to a hospital for medical reasons. This may or may not be overnight. It does not include presentation at a casualty or emergency room unless the event meets one of the other criteria for being an SAE.
- With regard to the criteria for an important medical event, medical and scientific judgment should be used in deciding whether prompt reporting is appropriate in this situation.

7.2.1.6 Reporting of Serious Adverse Events

All SAEs occurring up to 30 days following the last dose of study medication must be reported to the sponsor, regardless of whether they are suspected of having a causal relationship with the study drug. Any SAEs for which the investigator does suspect a causal relationship must be reported to the sponsor regardless of the time elapsed since the last dose of the study drug.

Patients will be instructed to report SAEs to the investigator within 24 hours, by telephone. In turn, the investigator must report all SAEs to the sponsor within 24 hours of occurrence or notification by the patient, using the sponsor's SAE form. The sponsor will provide contact information for reporting SAEs. An assessment of causality must be provided at the time of the initial report. The investigator or delegate must then complete and submit a follow-up SAE form to the sponsor within 5 calendar days, and must submit further follow-up forms if additional relevant follow-up information becomes available.

The sponsor will submit reports of SAEs to the appropriate regulatory agencies, in line with local regulatory requirements and timelines.

Investigators must report all SAEs to their IRB/IEC, as per local policy, as well as to the sponsor. If any SAE that is considered at least possibly related to the study medication and is unexpected occurs at one site, the sponsor will promptly inform all other sites of this, and all investigators must then report this event to their own IRBs/IECs, following the same timelines as above or following local IRB/IEC policy, whichever takes precedence.

7.2.1.7 Follow-up and Documentation of SAEs

SAEs that occur during the study and up to 30 days after the last dose of study drug must be documented in the patient's medical record and on the SAE report form. The investigator should attempt to establish a diagnosis of the event based on signs, symptoms, and/or other clinical information. In such cases, the diagnosis rather than the individual signs/symptoms should be documented as the SAE.

All SAEs must be followed until resolution, the condition stabilizes, the event is otherwise explained, or the patient is lost to follow-up. The investigator is responsible for ensuring that follow-up includes any supplemental investigations that may be indicated, in order to elucidate the nature and/or causality of the SAE as completely as possible. This may include additional laboratory tests or investigations, histopathological examinations, or consultation with other health care professionals. The sponsor may request that the investigator perform or arrange for the conduct of supplemental measurements and/or evaluations.

If a patient dies during participation in the study or during a specified follow-up period, the sponsor should be sent a copy of any post-mortem findings, including histopathology.

New or updated information is to be recorded on a new SAE report form, indicated as follow-up, and signed and dated by the investigator.

The clinical research associate (CRA) will verify the original SAE report form against the source documents at the next monitoring visit.

7.2.1.8 Adverse Events of Special Interest

7.2.1.8.1 Neutropenia

Individuals taking deferiprone must be monitored for neutropenia, defined as a confirmed absolute neutrophil count (ANC) less than 1.5×10^9 /L. Categories of neutropenia are as follows:

Category	Black Population	All Other Races
Mild	A confirmed ANC $< 1.0 \times 10^9/L$ but $\ge 0.65 \times 10^9/L$	A confirmed ANC $< 1.5 \times 10^9$ /L but $\ge 1.0 \times 10^9$ /L
Moderate	A confirmed ANC $< 0.65 \times 10^9/L$ but $\ge 0.5 \times 10^9/L$	A confirmed ANC $< 1.0 \times 10^9$ /L but $\ge 0.5 \times 10^9$ /L
Severe/agranulocytosis	A confirmed ANC $< 0.5 \times 10^9 / L$	

For a case of neutropenia to be confirmed, there must be 2 consecutive counts, a maximum of 3 days apart, that are both less than the specified value. If the 2 counts are not in the same severity category, a third count will be required to determine the severity. If a patient has just a single ANC value less than $1.5 \times 10^9/L$ ($< 1.0 \times 10^9/L$ for a black patient), this is to be documented in the CRF as an AE of "decreased ANC", but is not to be defined as neutropenia. The investigator is to use judgment as to whether the decrease is clinically significant.

In addition to having ANC monitored, patients will be advised to immediately report any symptoms indicative of infection such as fever (≥ 38.5 °C), sore throat, and flu-like symptoms at any time during treatment or during the first week following treatment. They will be

provided with an emergency services card with contact information, and advised to carry it with them at all times.

Depending of the severity of neutropenia, patients will either remain in or be withdrawn from the study. The management of different severities of neutropenia is described below.

Mild and moderate neutropenia:

A patient who develops either mild or moderate neutropenia is to interrupt treatment as soon as the neutropenia is confirmed, and ANC is to be monitored every 2 days until resolution.

The patient should re-initiate treatment once the event is resolved, defined as 2 consecutive ANC $\geq 1.5 \times 10^9$ /L (ANC $\geq 1.0 \times 10^9$ /L for a black patient). If ANC is still $< 1.5 \times 10^9$ /L after 14 days, the investigator is to do the following:

- Withdraw patient from the study and monitor him/her until resolution of the event
- Advise patient regarding protective isolation
- Examine patient the same day (if possible), including drug history and physical examination
- Notify ApoPharma Inc. using the SAE form

Severe neutropenia/agranulocytosis:

A patient in whom a single ANC measurement $< 0.5 \times 10^9 / L$ is detected is to immediately stop treatment, without waiting for confirmation of the count, and a second measurement is to be done the following day. If the second ANC is still $< 0.5 \times 10^9 / L$, the patient is to be permanently withdrawn from the study, and ANC is to be monitored daily until resolution. The following procedures should be done by the investigator or the treating physician, as appropriate:

- Provide protective isolation; if clinically indicated, admit patient to hospital and obtain vital signs every 4 hours
- Examine the patient the same day, if possible, including drug history and physical examination
- With the patient's consent, collect a blood sample to attempt to identify genetic or other biomarkers related to agranulocytosis
- Notify ApoPharma Inc. using the SAE form.

The following additional measures describe a suggested medical management and monitoring:

- If possible, consider obtaining bone marrow aspirate for:
 - Histology
 - Progenitor culture
 - o Frozen storage (1 mL sample)
- If possible, consider obtaining bone marrow biopsy (minimum length 3 mm)
- Perform septic work-up including chest X-ray, blood, urine, and throat cultures
- Obtain q4h temperatures from patient (monitored by family at home if patient is not in the hospital)
- If warranted, administer granulocyte stimulating factors, such as G-CSF 10 μ g/kg, on an in-patient basis if possible, beginning the same day that the ANC is confirmed as $< 0.5 \times 10^9$ /L; administer daily until ANC is $> 1.5 \times 10^9$ /L on 2 consecutive days
- If ANC < 0.5 x 10⁹/L for 7 days, repeat bone marrow biopsy and aspirate weekly during the period of agranulocytosis, if warranted

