 - At the next visit, bring back the completed diary card plus all medication containers, whether empty, partly used, or unopened
 - In the event of a decision to withdraw from the study before completion, return to the clinic for an Early Termination Visit as soon as possible, and no later than one month following the last dose of study medication
- Schedule next study visit.

Weekly Blood Draws (every 7 ± 3 days except on weeks that include a study visit)

Patients must provide a weekly blood sample for hematology testing. The results should be reviewed by the investigator as soon as they are received, preferably within 24 hours.

Note: This procedure may be done either at a local laboratory or at the study site, or, with sponsor approval, at the patient's home by a visiting study nurse.

Month 1 (\pm 5 days)

Note: Since this visit will include pre-dose blood sampling for PK testing in a subset of patients, those individuals must be reminded beforehand to **not** take their morning dose that day before coming to the site, and to have fasted for at least 10 hours rather than 8. (They will be allowed to eat about 1.5 hours after dosing.) In addition, those who agreed to take part in the extensive PK testing need to be reminded that this visit will involve an all-day stay at the site.

- Collect blood samples for the following assessments:
 - Hematology and blood chemistry (including fasting glucose)
 - Pregnancy testing for all females of childbearing potential (a negative result is required for study continuation)
 - Subset of patients who have agreed to undergo extensive PK testing: Pre-dose PK sample
- Administer morning dose of study medication, and note the time at which it was given
- Subset of patients who have agreed to undergo extensive PK testing: Collect blood samples at 0.25, 0.5, 0.75, 1.0, 1.33, 1.66, 2.0, 2.33, 2.66, 3.0, 3.5, 4.0, 5.0, 6.0, 8.0, 10.0, and 12.0 hours post-dose
- Complete the C-SSRS
- Verify treatment compliance through review of patient diary card and tablet count, and confirm that the patient has enough medication to last until the next visit
- Additionally review diary card for information on adverse events and use of concomitant medications, and file the diary card with the source documents
- Measure vital signs, first in the supine and then in the standing position (single measurement for each) and body temperature
- Conduct contraceptive counseling if applicable

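### A first ANC of 0.5 to < 1.5 x 10^9/L without fever or infection: interruption needs a second low count within 3 days, but no sentence orders that count and the weekly schedule does not reliably supply it

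*Protocol*

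**What the plan says.** Protocol Section 7.2.1.8.1 defines confirmation: "For a case of neutropenia to be confirmed, there must be 2 consecutive counts, a maximum of 3 days apart", both below the threshold. If the two counts fall in different severity categories, "a third count will be required to determine the severity". A patient with mild or moderate neutropenia "is to interrupt treatment as soon as the neutropenia is confirmed", and the same sentence starts ANC checks every 2 days.

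For one low value, the section asks for an adverse event entry of decreased ANC and adds: "The investigator is to use judgment as to whether the decrease is clinically significant".

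The branch below 0.5 x 10^9/L is worded differently. The patient is to "immediately stop treatment, without waiting for confirmation of the count", and "a second measurement is to be done the following day".

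Section 5.1 sets the routine schedule as "Weekly Blood Draws (every 7 ± 3 days except on weeks that include a study visit" and says of the results: "The results should be reviewed by the investigator as soon as they are received, preferably within 24 hours". Table 5.1 gives the same schedule as weekly with a ± 3 day allowance.

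Sections 4.5.3 and 7.2.1.8.2 require immediate interruption for fever or infection, with counts every 2 days if the ANC is low.

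**The concern.** The rule that stops drug in mild and moderate neutropenia depends on a pair of counts that the routine schedule is not built to produce. The count that would complete the pair is implied but never ordered.

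Suppose a patient without fever has an ANC of 0.8 and, a week later, 0.7. These counts are too far apart to be confirmed neutropenia. They are also no longer a single low value. Section 7.2.1.8.1 gives no management rule for this patient. A site that inferred the repeat could have interrupted drug within days. A site that follows the words alone could continue dosing.

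Section 1.4 names severe neutropenia or agranulocytosis as the most serious known risk of deferiprone, seen in about 2% of patients in pooled trials. It gives early detection of a falling ANC as the purpose of weekly testing. Whether drug is stopped should not depend on how a site reads a case definition. The later steps for a low ANC that persists at 14 days (withdrawal, isolation advice, examination, notice on the SAE form) sit under the same confirmed-case rule, so they depend on it too.

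**Working it through.** **Inputs.** Confirmation limit: 3 days (Section 7.2.1.8.1). Routine interval: 7 ± 3 days (Section 5.1). Dosing: twice daily, so 2 doses per day. Affected range: first ANC of 0.5 to < 1.5 x 10^9/L, or 0.5 to < 1.0 for Black patients, without fever or infection.

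**1. Interval as Section 5.1 words it.** Shortest gap 7 − 3 = 4 days; longest 7 + 3 = 10 days. Since 4 > 3, no pair of successive weekly draws meets the limit. The shortest gap is 1 day too long.

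**2. Other reading: a window around fixed weekly dates (possible from Table 5.1).** If one draw is shifted by a days and the next by b days, each from −3 to +3, the gap is 7 + b − a. The range is 7 − 3 − 3 = 1 day to 7 + 3 + 3 = 13 days. The limit is met when b − a ≤ −4, which holds for 3 + 2 + 1 = 6 of the 7 x 7 = 49 day combinations. A draw next to a study visit, which has its own ± 5 day window, may also fall within 3 days. In either case confirmation comes from scheduling chance and not from a rule.

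**3. Is a repeat ordered anywhere?**

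| Situation | What the protocol orders | Timing of next count |
|---|---|---|
| ANC < 0.5 | stop at once, second count | next day |
| Fever or infection | stop at once, more frequent counts | every 2 days if ANC is low |
| Two counts in different categories | third count | not stated; needs two counts already |
| First ANC in the affected range, no fever or infection | adverse event entry, judgment of significance | none stated |

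Sections 5.1 and 7.2.2 require prompt review of results, not a repeat. The adverse event follow-up duty in Section 7.2.1.2 requires the investigations needed to elucidate the event, but names no ANC repeat and sets no time.

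**4. Doses between draws, excluding result turnaround.** To a repeat within 3 days: at most 3 x 2 = 6. To the next weekly draw (Section 5.1 wording): 4 x 2 = 8 to 10 x 2 = 20. A low result at that weekly draw still does not meet the stated trigger.

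**The case against.** The strongest reply is that the repeat is already required in substance. Section 7.2.1.8.1 opens by saying that patients must be monitored for neutropenia, and it defines neutropenia by a confirmed count. If weekly draws cannot confirm it, meeting that duty takes a further count. Section 7.2.1.2 makes the investigator responsible for the investigations needed to elucidate an adverse event, and whether a low ANC is isolated or is neutropenia can be settled only within 3 days. The third-count rule and the words about not waiting for confirmation both assume that a confirmatory draw takes place.

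Much of this stands. The definition does imply a repeat, and most sites would do one. But the duty has to be assembled from several sections, whereas the branch below 0.5 states it in one clause. It also leaves open what to do when the repeat is missed or late: two low weekly counts then trigger nothing, whatever was intended.

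A reader might infer three stronger points that the protocol does not support:

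- That weekly draws can never confirm a case. This fails under the fixed-window reading and next to study visits.
- That patients would stay on drug through a run of low counts. This assumes no clinical action at all, despite prompt review and a required judgment of significance; nothing in the protocol suggests that as expected conduct.
- That severe neutropenia or infection is left uncovered. Both are acted on without confirmation and are outside this point.

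The 6 doses are also not a ceiling on doses before interruption, because interruption follows the result of the second count, not the draw.

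**Conclusion.** The point holds as a cheap improvement for patient safety. In the affected range, the protocol makes interruption and 2-day monitoring depend on a count that it implies but does not order, and the routine schedule supplies that count only by chance or not at all. As written, two successive low weekly counts do not trigger interruption.

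The size is the difference between at most 6 doses and 8 to 20 doses between draws, plus the missing rule after a second low weekly count. The 8 to 20 rests on the Section 5.1 wording of the interval. The protocol gives no basis for estimating how many patients would be affected. This is a patient-management rule, so it belongs in the protocol and cannot be left to an analysis plan.

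**What to change.** Add two sentences to Section 7.2.1.8.1 and repeat them in the weekly-draw note of Section 5.1:

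1. Any single ANC of 0.5 to < 1.5 x 10^9/L (0.5 to < 1.0 for Black patients) must be repeated within 3 days.
2. If that repeat was missed or late and the next count is also low, study drug is interrupted and ANC is checked every 2 days; the existing resolution, 14-day withdrawal and SAE-form rules run from that interruption as for confirmed neutropenia.

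Item 2 is a management rule, so the case definition for adverse event reporting can stay as it is.

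The cost is some extra blood counts and a few more interruptions. As a rough scale, 140 patients x 39 weeks = 5,460 scheduled counts with no dropout. If 0.5% to 2% fell in this range (an assumption; the protocol gives no figure), that is 5,460 x 0.005 ≈ 27 to 5,460 x 0.02 ≈ 109 extra draws over the whole study. Section 5.5 already exempts under-compliance caused by interruption for neutropenia from being reported as a deviation. It would help to state that interruptions under item 2 are treated the same way.

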4.2 Inclusion Criteria

Individuals will be eligible to enroll in the study if they meet all the following criteria:

- 1. Male or female aged \geq 18 to <80 years
- 2. Body weight \geq 60 kg but \leq 100 kg
- 3. Diagnosis of Parkinson's disease according to UK Parkinson's Disease Society Brain Bank Clinical Diagnostic Criteria and based on the presence of at least two of the three cardinal features of the disease (rest tremor, bradykinesia, and rigidity). If rest tremor is not present, patient must have unilateral onset of symptoms.
- 4. Absolute neutrophil count $\ge 1.5 \times 10^9 / L$ ($\ge 1.0 \times 10^9 / L$ for Black population) at screening
- 5. On a stable dose for at least 3 months prior to the screening visit of any of the following treatments at an L-dopa equivalent daily dose of up to 600 mg:
 - o Dopaminergic agonist alone
 - L-dopa alone
 - o Combination therapy with dopaminergic agonist and L-dopa
 - o Rasagiline
- 6. At an early stage of the disease, without motor fluctuations and/or L-dopa—induced dyskinesia
- 7. A female patient must meet one of the following criteria:
 - If of childbearing potential, have a negative pregnancy test result at screening. In addition, she must:
 - Agree to use an effective method of contraception according to local requirements, during the study and for 30 days following the last dose of study medication, OR
 - b. Have undergone a tubal ligation (supporting evidence required), OR
 - c. Abstain from heterosexual intercourse, OR
 - d. Have a male sexual partner who has been sterilized (supporting evidence required)
 - Be of non-childbearing potential, defined as surgically sterile, having undergone complete hysterectomy or bilateral oophorectomy (supporting evidence required) or

being in a menopausal state (being 50 years of age or older and at least 1 year without menses)

- 8. Fertile heterosexual males must agree to use an effective method of contraception during the study and for 30 days following their last dose of study medication
- 9. All patients and/or their authorized legal representatives must provide signed and dated written informed consent prior to the first study intervention, and patients must be able to adhere to study restrictions, appointments, and evaluation schedules

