All AEs must be followed until resolution, the condition stabilizes, the event is otherwise explained, or the patient is lost to follow-up. The investigator is responsible for ensuring that follow-up includes any supplemental investigations that are needed to elucidate the nature and/or causality of the AE as completely as possible. This may include additional laboratory tests or investigations, histopathological examinations, or consultation with other health care professionals.

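### The 14-day withdrawal rule for mild or moderate neutropenia omits the lower ANC threshold that the protocol uses for Black patients everywhere else it matters

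*Protocol*

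**What the plan says.** All values are ANC in units of 10⁹/L.

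- **Entry.** Protocol section 4.2, criterion 4, requires at least 1.5, but only 1.0 "for Black population) at screening". A Black patient can therefore enter the trial at 1.0 to below 1.5.
- **Opening definition.** Section 7.2.1.8.1 begins: "Individuals taking deferiprone must be monitored for neutropenia, defined as a confirmed absolute neutrophil count (ANC) less than" 1.5, with no separate value for Black patients.
- **Category table.** Directly below, mild neutropenia is 1.0 to below 1.5 for all other races and 0.65 to below 1.0 for Black patients.
- **Single low count.** The limit is 1.5, or 1.0 for a Black patient.
- **Mild or moderate event.** The patient "is to interrupt treatment as soon as the neutropenia is confirmed", and counts are then taken every 2 days.
- **Resolution.** "The patient should re-initiate treatment once the event is resolved, defined as 2 consecutive ANC" values of at least 1.5, or at least 1.0 for a Black patient.
- **14-day rule.** The next sentence applies if the ANC is still below 1.5 "after 14 days, the investigator is to do the following". The first action is "Withdraw patient from the study and monitor him/her until resolution of the event". The others are advice on protective isolation, a same-day examination if possible, and notification of the sponsor on the SAE form. No value is given for Black patients.

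The infection rules in sections 4.5.3 and 7.2.1.8.2 and exclusion criterion 13 in section 4.3 also give the 1.0 value.

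**The concern.** The 14-day rule decides whether a patient leaves the trial, and it uses a limit that the rest of the section does not apply to Black patients. For them, a count of 1.0 to below 1.5 lies in no neutropenia category, counts towards resolution and is acceptable at entry. Under the 14-day sentence the same count leads to withdrawal. The limit of 1.5 can even exceed the patient's own screening value.

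At stake for such a patient are an unnecessary permanent withdrawal (section 4.5.2 says withdrawn patients are not replaced) and an SAE form for an event that may meet the protocol's definition of resolution at the next count. Neutropenia is the risk behind the weekly blood draws, so sites should not have to infer which limit governs a mandatory stop.

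**Working it through.** The protocol states no figure to reproduce. The check compares thresholds, works through one timing case and bounds the number affected.

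**1. Thresholds side by side (10⁹/L)**

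| Rule | Other races | Black patients |
|---|---|---|
| Eligibility (4.2, criterion 4) | ≥1.5 | ≥1.0 |
| Opening definition (7.2.1.8.1) | <1.5 | not given |
| Upper limit of mild category (table) | <1.5 | <1.0 |
| Single low count | <1.5 | <1.0 |
| Resolution, two consecutive counts | ≥1.5 | ≥1.0 |
| Withdrawal after 14 days | <1.5 | not given |

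Two rows lack the second value. The table that follows the opening definition corrects it. Nothing that follows corrects the 14-day rule.

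**2. Who is caught**

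I take day 0 as the day of confirmation; the protocol does not say when the 14 days start. Counts every 2 days fall on days 2, 4, 6, 8, 10, 12 and 14, which is 7 counts. Two consecutive qualifying counts by day 14 require the first of them by day 12.

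- *Black patient, first count of at least 1.0 on day 14, say 1.2.* There is only one qualifying count, so the event is unresolved. The count is below 1.5, so as written the patient is withdrawn and the SAE form is sent. A count of at least 1.0 on day 16 would have resolved the event.
- *Patient of another race, first count of at least 1.5 on day 14, say 1.6.* There is again only one qualifying count and the event is unresolved. The count is not below 1.5, so the patient is not withdrawn.

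Both patients have just reached their own recovery threshold, and only one must leave. Day 14 need not be the first recovered count. A Black patient with 1.1 on day 10, 0.9 on day 12 and 1.2 on day 14 also has no two consecutive qualifying counts and is also withdrawn.

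**3. How many**

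The protocol gives neither the share of Black patients nor a rate of mild or moderate neutropenia. I assume 2% to 10% for each and apply them to the 112 patients planned for active drug:

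- low: 112 × 0.02 × 0.02 = 0.04 events
- high: 112 × 0.10 × 0.10 = 1.1 events

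These are all mild or moderate events in Black patients on active drug. Only those unresolved at day 14 with a count of 1.0 to below 1.5 are affected. At the high end, 1 ÷ 1.12 = 0.89, so the expected number stays below one patient unless about 89% or more of the events end in that situation.

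**The case against.** The strongest reply is that a sensible investigator would read the rule correctly. The race-specific value stands in the sentence immediately before it, and the wording of the rule limits it to events that have not resolved. Much of this stands. A reader might infer that a Black patient with two consecutive counts of 1.2 who has already restarted treatment must be withdrawn on day 14. The text does not support that. The word still, and the instruction "Withdraw patient from the study and monitor him/her until resolution of the event", tie the rule to unresolved events, and this patient's event has resolved. The reply does not dispose of the unresolved patient in step 2, for whom the only number printed is 1.5.

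A reader might also infer that no time limit exists for repeating a low but non-severe count. The section does not bear that out. For confirmation, "there must be 2 consecutive counts, a maximum of 3 days apart, that are both less than the specified value". A limit shorter than the weekly draw interval implies an unscheduled repeat. Results are to be reviewed promptly (sections 5.1 and 7.2.2), and section 7.2.1.2 adds: "All AEs must be followed until resolution, the condition stabilizes, the event is otherwise explained, or the patient is lost to follow-up". Only a separate order to repeat the count is absent, which is a matter of detail.

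Finally, the slip is conservative and rare. That is correct, and it sets the grade.

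**Conclusion.** The omission is real: as written, the 14-day rule applies the wrong threshold to Black patients whose event is unresolved and whose count on day 14 is 1.0 to below 1.5. This is an internal inconsistency. The thresholds themselves are not in question.

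The severity is minor. The affected group is narrow and probably amounts to fewer than one patient. That figure rests on the assumed 2% to 10% rates, and the share of events in the day-14 situation is not quantified. The two-day counting in step 2 also assumes that day 0 is the day of confirmation.

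A reader might infer that Black patients are under-protected or that the trial's results are at risk. Neither follows. The error withdraws too readily, the separate rule for counts below 0.5 × 10⁹/L is the same for all races and is untouched, and the analysis of the primary endpoint does not change.

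**What to change.** In Protocol section 7.2.1.8.1, insert (< 1.0 × 10⁹/L for a black patient) after the 1.5 value in the 14-day sentence. For consistency, add the same parenthesis to the opening definition of neutropenia in that section.

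The cost is two parentheses in one section, using a threshold already in the protocol. Design, sample size, visit schedule and analysis do not change.
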